4. OBJECTIVES AND ENDPOINTS

Objectives	Endpoints
Primary	

 To determine total radioactivity (drug related material) in plasma following a single IV microtracer of [¹⁴C]-GSK2269557 (concomitant with an inhaled non-radiolabelled GSK2269557 dose) and a single oral dose of [¹⁴C]-GSK2269557. 	
 AUC(0-inf), AUC(0-t), Cmax, tmax, t_{1/2} of total drug-related material (radioactivity) in plasma.

 To determine the rate and extent of excretion of total radioactivity in urine and faeces and the total recovery of radioactivity following a single IV microtracer of [¹⁴C]-GSK2269557 (concomitant with an inhaled non-radiolabelled dose) and a single oral dose of [¹⁴C]-GSK2269557. 	
 Urinary and faecal cumulative excretion as a percentage of the total radioactive dose administered over time.
Secondary	

 To determine parent GSK2269557 concentration in plasma following a single IV microtracer of [¹⁴C]-GSK2269557 (concomitant with an inhaled non-radiolabelled GSK2269557 dose) and a single oral dose of [¹⁴C]-GSK2269557. 	
 AUC(0-inf), AUC(0-t), Cmax, tmax, and t_{1/2} of parent GSK2269557 and [¹⁴C]-GSK2269557¹ in plasma. Volume and clearance of parent [¹⁴C]-GSK2269557¹ after IV dose only.

 To estimate the absolute bioavailability of GSK2269557 following inhaled and oral administration. 	
 Oral and inhaled F (absolute bioavailability).

Objectives	Endpoints

 To evaluate the safety and tolerability of GSK2269557 after single IV, oral and inhaled doses in healthy participants. 	
 Incidence of adverse events Laboratory safety, electrocardiogram (ECG) and vital signs parameters.
Exploratory	

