### 2.2. Study Objective(s) and Endpoint(s)

Objective	Endpoint
Primary	

 
• To determine total radioactivity (drug related material) in plasma following a single IV microtracer of [C]-GSK2269557 (concomitant with an inhaled non-radiolabelled GSK2269557 dose) and a single oral dose of [C]-GSK2269557.
 
	
 
• AUC (0-inf), AUC (0-t), Cmax, tmax, t1/2 of total drug-related material (radioactivity) in plasma.
 

 
• To determine the rate and extent of excretion of total radioactivity in urine and faeces and the total recovery of radioactivity following a single IV microtracer of [C]-GSK2269557 (concomitant with an inhaled non-radiolabelled dose) and a single oral dose of [C]-GSK2269557.
 
	
 
• Urinary and faecal cumulative excretion as a percentage of the total radioactive dose administered over time.
 

Objective	Endpoint
Secondary	

 
To determine parent GSK2269557 concentration in plasma following a single IV microtracer of [C]-GSK2269557 concomitant with an inhaled non-radiolabelled GSK2269557 dose and a single oral dose of [C]-GSK2269557.
 
	
 
AUC(0-inf), AUC(0-t), Cmax, tmax, and t1/2 of parent GSK2269557 and [C]-GSK2269557 in plasma.
 
Volume and clearance of parent [C]-GSK2269557 after IV dose only.
 

 
To estimate the absolute bioavailability of GSK2269557 following inhaled and oral administration.
 
	
 
Oral and inhaled F (absolute bioavailability).
 

 
To evaluate the safety and tolerability of GSK2269557 after single IV, oral and inhaled doses in healthy participants.
 
	
 
Incidence of adverse events.
 
Laboratory safety, electrocardiogram (ECG) and vital signs parameters.
 

Exploratory	

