**Table 2** **Derived Urine and Faeces Pharmacokinetic Parameters**

Parameter	Parameter Description
Ae[urine]	Total radioactivity recovered in the urine (Ae[urine]) calculated for each collection interval per subject and treatment period as:  Ae[urine]=(concentration in urine sample x collected sample weight) for each urine collection interval, eg 0-6, 6-24, 24-48, etc.
Cumulative Ae[urine]	Cumulative total radioactivity recovered in the urine (Cumulative Ae[urine]) calculated for each cumulative collection interval per subject and treatment period as:  Cumulative Ae[urine]= summation of Ae[urine] for each urine collection within the cumulative urine collection interval, eg 0-24, 0-48, etc.
Fe%[urine]	% of total dose excreted as total radioactivity (Fe%[urine]) for each collection interval per subject and treatment period, will be estimated as:  Fe%[urine]=(Ae[urine]) for each collection period)/Dose*100.  Where the dose is the radiolabelled [  C]-GSK2269557, that is in period 1 radiometric iv dose, in period 2 radiometric oral dose
Cumulative Fe%[urine]	Cumulative % of total dose excreted as total radioactivity (Cumulative Fe%[urine]) for each cumulative collection interval per subject and treatment period, will be estimated as:  Cumulative Fe%[urine]=summation of Fe%[urine] for each urine collection within the cumulative urine collection interval, eg 0-24, 0-48, etc.

Parameter	Parameter Description
Ae[faeces]	
Total radioactivity recovered in the faeces (Ae[faeces]) calculated for each collection interval per subject and treatment period as
 $Ae[\text{faeces}] = (\text{concentration in faecal homogenate aliquot analysed} \times \text{weight of homogenate aliquot analysed}) \times (\text{total homogenate weight} / \text{collected sample weight})$ 
for each faecal collection interval, eg 0-24, 24-48, etc

Cumulative Ae[faeces]	
Cumulative total radioactivity recovered in the faeces (Cumulative Ae[faeces]) calculated for each cumulative collection interval per subject and treatment period as
 $\text{Cumulative Ae}[\text{faeces}] = \text{summation of Ae}[\text{faeces}]$ 
for each faecal collection within the cumulative faecal collection interval, eg 0-24, 0-48, etc

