### **8.2.2. Summary Measure**

A primary objective is to determine total radioactivity (drug related material) in plasma following a single IV microtracer of [14C]-GSK2269557 (concomitant with an inhaled non-radiolabelled GSK2269557 dose) and a single oral dose of [14C]-GSK2269557. To assess this, the plasma PK parameters: AUC (0-inf), AUC (0-t), AUC (0-24), %AUCex, Cmax, tmax, t1/2 of total drug-related material (radioactivity) will be summarised and listed.

The additional primary objective is to determine the rate and extent of excretion of total radioactivity in urine and faeces and the total recovery of radioactivity following a single IV microtracer of [14C]-GSK2269557 (concomitant with an inhaled non-radiolabelled dose) and a single oral dose of [14C]-GSK2269557. To assess this, the PK parameters: Ae and Fe% will be summarised and listed for urine faeces and total (Urine + Faeces).

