6. Sampling times relative to the start of the IV infusion. Blood samples for total radioactivity, [C]-GSK2269557 analysis and cold GSK2269557 analysis will be taken: pre-dose and at 0h (post inhalation and pre-IV infusion), at the end of infusion and at 0.33, 0.5, 0.75, 1, 2, 3, 4, 6, 8, 12, 16, 24, 48, 72, 96 and 168 h after the start of infusion.
7. Background radiation sample taken at screening, Day -1 and pre-dose only.
8. An additional pre-dose blood sample may be taken from 1 participant for preparation of a plasma shipment control (details provided in the SRM).
9. Blood samples for plasma metabolite profiling will be collected at 0.5 h and 4 h after the start of the IV infusion.
10. An aliquot from each urine collection will be taken for metabolic profiling (separate study).
11. Sampling times relative to the start of the IV infusion. Urine will be collected at pre-dose, 0-6 h, 6-24 h then over 24 h collection periods as follows: 24-48 h, 48-72 h, 72-96 h, 96-120 h, 120-144 h, 144-168 h.
12. An aliquot from each homogenised faecal collection will be taken for metabolic profiling (separate study).
13. Sampling times relative to the start of IV infusion The pre-dose faecal collection sample can be collected up to 24 h pre-dose. Afterward faeces will be collected over 24 h collection periods as follows: 0-24 h, 24-48 h, 48-72 h, 72-96 h, 96-120 h, 120-144 h, 144-168h.
14. Entero-Test string device will be swallowed at approximately 3.5 h pre-dose (start of inhaled dose) while participants are in a fasted state and the string removed at about 2.5 h post-dose on Day 1. At about 0.5 h post-dose (i.e. 2 hours before string withdrawal) a food cue will be used to stimulate gall bladder emptying).
15. Meal times are 30 min, 4 h and 10 h post dose on Day 1. On all other days, meals will be served at the standard times for the unit.
16. AEs and SAEs will be collected from the signing of the ICF until the follow-up visit. However, any SAEs related to study participation or a GSK concomitant medication will be recorded from the time a participant consents to participate in the study and until the final follow-up visit contact.

## Schedule of activities for treatment period 2

Procedure	Treatment Period 2 (Oral dosing)									Follow-up (7-14 days post-last dose) 	
	Day										
	-1	1 		2	3	4	5	6	7		
		Pre-dose	Post-dose 0-16 h	24 h	48 h	72 h	96 h	120 h	144 h	168 h	
Admission to Unit	X										

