2.7.	PK	PK16a	Individual Subject Plasma GSK2269557 Concentration-time Plot (Linear and Semi-log) by Treatment	Linear and log plot on same page. Separate page per treatment. N (likely 6) lines for each treatment with legend to identify subjects Time = Planned time post dose (h) Include the LLOQ as a reference line and footnote  refer to GSK961081/mid201003/final/f_pk_21	SAC
2.8.	PK	PK19	Arithmetic Mean (+SD) Plasma GSK2269557 Concentration-time Plot (Linear and Semi-log) by Treatment	Linear and log plot on same page. Separate page per treatment. Time = Planned time post dose (h) Include the LLOQ as a reference line and footnote  refer to GSK961081/ mid201003/ final/ f_pk_22	SAC
2.9.	PK	PK20	Median (Range) Plasma GSK2269557 Concentration-time Plot (Linear and Semi-log) by Treatment	Linear and log plot on same page. Separate page per treatment. Time = Planned time post dose (h) Include the LLOQ as a reference line and footnote  refer to GSK961081/ mid201003/ final/ f_pk_23	SAC

Pharmacokinetic: Figures					
No.	Population	IDSL / TST ID / Example Shell	Title	Programming Notes	Deliverable
Urine and Faeces					
2.10.	PK	PK_F4	Individual Subject Absolute –Total Radioactivity Recovered (Amount Excreted) for Urine, Faeces and Total Excretion by Time and Treatment	Ae(urine), Ae(faeces), Ae(total). Linear scale only. Separate page per subject and treatment. 3 lines per plot with legend to identify Urine Faeces and Total Excretion Time = actual mid-point of collection post dose (h).  refer to GSK961081/ mid201003/ final/ f_pk_210	SAC
2.11.	PK	PK_F5	Arithmetic Mean Absolute –Total Radioactivity Recovered (Amount Excreted) for Urine, Faeces and Total Excretion by Time and Treatment	Ae(urine), Ae(faeces), Ae(total). Linear scale only. Separate page per Treatment. 3 lines per plot with legend to identify Urine Faeces and Total Excretion Time = actual mid-point of collection post dose (h).  refer to GSK961081/ mid201003/ final/ f_pk_212	SAC

Pharmacokinetic: Figures					
No.	Population	IDSL / TST ID / Example Shell	Title	Programming Notes	Deliverable

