2.12.	PK	PK_F4	Individual Subject Cumulative –Total Radioactivity Recovered (Cumulative Amount Excreted) for Urine, Faeces and Total Excretion by Time and Treatment	Cumulative Ae(urine), Cumulative Ae(faeces), Cumulative Ae(total).  Linear scale only. Separate page per subject and treatment. 3 lines per plot with legend to identify Urine Faeces and Total Excretion Time = actual mid-point of collection post dose (h).  refer to GSK961081/ mid201003/ final/ f_pk_210	SAC
2.13.	PK	PK_F5	Arithmetic Mean Cumulative –Total Radioactivity Recovered (Cumulative Amount Excreted) for Urine, Faeces and Total Excretion by Time and Treatment	Cumulative Ae(urine), Cumulative Ae(faeces), Cumulative Ae(total).  Linear scale only. Separate page per Treatment. 3 lines per plot with legend to identify Urine Faeces and Total Excretion Time = actual mid-point of collection post dose (h).  refer to GSK961081/ mid201003/ final/ f_pk_212	SAC

Pharmacokinetic: Figures					
No.	Population	IDSL / TST ID / Example Shell	Title	Programming Notes	Deliverable
2.14.	PK	PK_F4	Individual Subject Absolute –Total Radioactivity Recovered (% of Dose) for Urine, Faeces and Total Excretion by Time and Treatment	Fe%(urine), Fe%(faeces), Fe%(total). Linear scale only. Separate page per subject and treatment. 3 lines per plot with legend to identify Urine Faeces and Total Excretion Time = actual mid-point of collection post dose (h). refer to GSK961081/ mid201003/ final/ f_pk_210	SAC
2.15.	PK	PK_F5	Arithmetic Mean Absolute –Total Radioactivity Recovered (% of Dose) for Urine, Faeces and Total Excretion by Time and Treatment	Fe%(urine), Fe%(faeces), Fe%(total). Linear scale only. Separate page per Treatment. 3 lines per plot with legend to identify Urine Faeces and Total Excretion Time = actual mid-point of collection post dose (h). refer to GSK961081/ mid201003/ final/ f_pk_212	SAC

Pharmacokinetic: Figures					
No.	Population	IDSL / TST ID / Example Shell	Title	Programming Notes	Deliverable
2.16.	PK	PK_F4	Individual Subject Cumulative –Total Radioactivity Recovered (Cumulative % of Dose) for Urine, Faeces and Total Excretion by Time and Treatment	Cumulative Fe%(urine), Cumulative Fe%(faeces), Cumulative Fe%(total). Linear scale only. Separate page per subject and treatment. 3 lines per plot with legend to identify Urine Faeces and Total Excretion Time = actual mid-point of collection post dose (h).  refer to GSK961081/ mid201003/ final/ f_pk_210	SAC

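### A primary objective asks for the rate of excretion, but the SAP derives no rate, and its interval plots put urine amounts from 6, 18 and 24 h collections on one unscaled axis

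*SAP*

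**What the plan says.** Protocol Section 4 sets as a primary objective "To determine the rate and extent of excretion of total radioactivity in urine and faeces", together with total recovery. SAP Section 8.2.2 repeats it ("The additional primary objective is to determine the rate and extent of excretion of total radioactivity in urine and faeces") and names the measures that answer it: "To assess this, the PK parameters: Ae and Fe% will be summarised and listed for urine faeces and total (Urine + Faeces". The endpoint paired with the objective is "Urinary and faecal cumulative excretion as a percentage of the total radioactive dose administered over time".

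SAP Table 2 defines Ae and Fe%, per interval and cumulatively, for urine, faeces and total. Urinary Ae is concentration times sample weight "for each urine collection interval, eg 0-6, 6-24, 24-48, etc". None of these quantities is divided by the length of the interval. Protocol Section 10.3.1 lists no rate either.

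The urine schedule for period 1 reads "Urine will be collected at pre-dose, 0-6 h, 6-24 h then over 24 h collection periods as follows: 24-48 h, 48-72 h", and so on in 24 h blocks; period 2 uses the same intervals. Faeces are collected in 24 h blocks from dosing in both periods.

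The programming note for Figure 2.10 is "Ae(urine), Ae(faeces), Ae(total). Linear scale only. Separate page per subject and treatment" and for Figure 2.14 "Fe%(urine), Fe%(faeces), Fe%(total). Linear scale only. Separate page per subject and treatment". Figures 2.11 and 2.15 are the arithmetic-mean counterparts. All four place the value at the actual mid-point of the collection. The cumulative figures (2.12, 2.13, 2.16, 2.17) use the same mid-point time axis.

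**The concern.** Extent is answered by the cumulative quantities. Rate has no parameter of its own, so a reader will look for it in the interval figures or in the slope of the cumulative figures.

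An amount plotted at the interval mid-point follows the layout of an excretion-rate plot, but without the division by interval length that makes such a plot comparable across intervals. With urine intervals of 6, 18 and 24 h, the shape of the urine curve over the first two days partly reflects how long each collection ran. At stake is the reading of how quickly radioactivity leaves in urine: a falling rate may look like a rise and fall, or like a plateau.

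The total line has a separate gap. Ae[total] is urine plus faeces by collection interval, but on day 1 urine has two intervals and faeces one, and no pooling rule is given.

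**Working it through.** **Inputs from the documents.** Urine intervals 0-6, 6-24, 24-48 h and so on (SAP Section 11.2.1): widths 6, 18, 24 h; mid-points 3, 15, 36 h. The documents give no excretion rate or half-life, so there is no stated figure to reproduce. The half-lives below are assumptions, shown over a range.

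**Step 1: distortion that needs no half-life.** Plotted amount = mean rate × width. Against the 0-6 h point, the 6-24 h point is scaled by 18/6 = 3 and each 24 h point by 24/6 = 4. At a constant rate the plotted points rise 1 : 3 : 4.

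**Step 2: when the plot shows a peak that the rate does not have.** Assume mono-exponential excretion, k = ln 2 / half-life. The share of the excreted total in interval (a, b) is exp(-ka) - exp(-kb), and the mean rate is that share divided by (b - a).

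- 6-24 h exceeds 0-6 h: with x = exp(-6k), equality requires 1 - 2x + x⁴ = 0, so x = 0.544 and the half-life is 6.8 h. The false peak appears above this value.
- 24-48 h exceeds 6-24 h: equality is at 50.2 h, above which the apparent peak moves to 24-48 h.

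| Assumed excretion | Plotted share, % (0-6, 6-24, 24-48 h) | Mean rate, %/h |
|---|---|---|
| Half-life 5 h | 56.5, 39.9, 3.5 | 9.41, 2.22, 0.14 |
| Half-life 12 h | 29.3, 45.7, 18.8 | 4.88, 2.54, 0.78 |
| Half-life 24 h | 15.9, 34.1, 25.0 | 2.65, 1.89, 1.04 |
| Half-life 72 h | 5.6, 15.0, 16.4 | 0.94, 0.83, 0.68 |
| 20% with half-life 2 h, 80% with 24 h | 30.2, 29.8, 20.0 | 5.0, 1.7, 0.8 |

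The rate falls throughout in every row. The plotted amount falls throughout at 5 h, peaks late at 12, 24 and 72 h, and looks flat over day 1 in the bi-exponential row, where the rate in fact drops about 3-fold (30.2/6 = 5.0 against 29.8/18 = 1.7 %/h).

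**Step 3: does the cumulative plot supply the rate?** A cumulative amount is reached at the end of its interval but is drawn at the mid-point. Plotted slope ÷ true mean rate = width ÷ distance between successive plotted times (starting from the origin):

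- 0-6 h: 6/3 = 2.0
- 6-24 h: 18/(15 - 3) = 1.5
- 24-48 h: 24/(36 - 15) = 1.14
- later blocks: 24/24 = 1.0

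With a 24 h half-life the slopes would read 5.30, 2.84 and 1.19 %/h where the true mean rates are 2.65, 1.89 and 1.04 %/h.

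**The case against.** The strongest reply is that the pre-specified endpoint is cumulative excretion over time, and the SAP delivers it in full: derived in Table 2, tabulated in Table 2.20, plotted in Figures 2.16 and 2.17, and listed in Listing 41. Its slope is a rate. The interval figures are labelled as amounts or percentages of dose, Tables 2.17 and 2.19 and Listings 40 and 41 let a reader divide by interval length, and the notes to Table 2 allow further parameters. This stands to the extent that no endpoint is left underived and the SAP does not depart from the protocol. A reader might infer that the rate objective goes wholly unaddressed; the documents do not support that. What the reply does not cover is that the cumulative figures also distort the early slopes (Step 3), and that a primary objective should not rely on readers doing the division.

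A reader might also infer that the figures will show a false delayed peak. The documents do not support that either, because it depends on an excretion pattern they do not give. With half-lives of 3 or 5 h there is no false peak. In the bi-exponential cases tried, with 20% to 70% excreted in a 2 h fast phase and a slow half-life of 12 to 48 h, the largest amount stays in 0-6 h. After oral dosing with a 2 h absorption half-life and a 24 h elimination half-life, a later peak would be real (1.57 then 2.00 %/h). The only hints come from plasma parent drug in the footnotes to Protocol Table 1 and point both ways: Day 7 AUC/Cmax is 85/5.3 = 16.0 h, while the period 1 prediction is 14.7/3.5 = 4.2 h. Neither is a half-life of radioactivity in urine.

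The scope is also narrow. Faecal intervals are equal, so faecal interval amounts are already proportional to nominal rate, and the analyses are descriptive.

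**Conclusion.** The point holds as a reporting gap. The objective names rate, no excretion rate is derived, and the interval figures mix urine collections of 6, 18 and 24 h without scaling. The 3-fold and 4-fold inflation relative to the 0-6 h point follows from the schedule alone. A spurious later peak is possible rather than certain: it requires a half-life above about 6.8 h if excretion is mono-exponential. Where an early fast phase prevents the peak, the plot can still conceal a fall in rate.

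In the interval figures the effect is limited to the first two urine intervals relative to the later ones, and to the day-1 total. Recovery totals, tabulated cumulative values and plasma parameters are unaffected. The mid-point placement in the cumulative figures is a related plotting fault that weakens the other graphical route to rate.

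**What to change.** - **SAP Table 2:** add urinary excretion rate = Ae[urine] / actual interval duration (h), and the matching Fe%[urine] per hour, for both periods. State that total is formed on 24 h blocks, pooling urine 0-6 h and 6-24 h on day 1, because faeces are collected 0-24 h.
- **Tables 2.17 and 2.19:** report the rates alongside the interval amounts and percentages.
- **Figures 2.10, 2.11, 2.14 and 2.15:** plot urine rate at the interval mid-point. If amounts are kept, pool urine to 0-24 h so that every point covers 24 h.
- **Figures 2.12, 2.13, 2.16 and 2.17:** plot cumulative values at the end of the interval.

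The cost is SAP wording and a few lines of programming. All the data needed are already planned for collection.

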### **8.2.3. Population of Interest**

The primary pharmacokinetic analyses will be based on the “Pharmacokinetic” population, unless otherwise specified.

### **8.2.4. Statistical Analyses / Methods**

Details of the planned displays are provided in [Appendix 9](#) List of Data Displays and will be based on GSK Data Standards and statistical principles.

Unless otherwise specified, endpoints / variables defined in Section [8.2.1](#) will be summarised using descriptive statistics, graphically presented (where appropriate) and listed.

## **8.3. Secondary Pharmacokinetic Analyses**

### **8.3.1. Endpoint / Variables**

#### **8.3.1.1. Drug Concentration Measures**

Refer to [Appendix 4](#) Data Display Standards & Handling Conventions (Section 11.4.3 Reporting Standards for Pharmacokinetic)

### 8.3.1.2. Derived Pharmacokinetic Parameters

Pharmacokinetic parameters will be calculated as described in Section 8.1.2.

### 8.3.2. Summary Measure

A secondary objective is to determine parent GSK2269557 concentration in plasma following a single IV microtracer of [C]-GSK2269557 (concomitant with an inhaled non-radiolabelled GSK2269557 dose) and a single oral dose of [C]-GSK2269557. To assess this, the plasma PK parameters: AUC (0-inf), AUC (0-t), AUC (0-24), %AUCex, Cmax, tmax, t1/2 of parent GSK2269557 ([C]-GSK2269557 and GSK2269557) will be summarised and listed and the volume (Vdss and Vc) and clearance of parent GSK2269557 ([C]-GSK2269557) after IV dose only will be summarised and listed.

Another secondary objective is to estimate the absolute bioavailability of GSK2269557 following inhaled and oral administration. To assess this, the oral and inhaled bioavailability (F) will be summarised and listed.

To assess metabolism, the plasma PK parameters: ML(iv), ML(po), Fg, EH, Fabs will be summarised and listed. To assess exposure and metabolite ratio in humans, the ratio of Parent GSK2269557/total radioactivity will be calculated for the plasma PK parameters: Cmax, AUC(0-t), AUC(0-24) and AUC(0-∞), results will be summarised, listed and statistical analyses will be conducted as described in Section 8.3.4.1. To assess renal clearance, the PK CLr will be summarised and listed if bioanalysis can quantify parent GSK2269557 in urine collection intervals (i.e. if Ae is quantifiable for collection intervals).

